8.1.3.3 Analysis of responder rate

The number and percentage of subjects achieving a Response, Complete Response and Platelet Count $\geq 50 \times 10^9/L$ will be summarized by dose arm at each scheduled post-Baseline visit. The 90% CI for the percentage of responders will be included, calculated using a Wilson approximation. The tabulation will also include an overall summary (across all visits) of the number and percentage of subjects achieving a Response, Complete Response and Platelet Count $\geq 50 \times 10^9/L$ at any time during the study. For the purpose of the tabulation the lower and upper 90% CI for the percentage of subjects will be truncated at 0 and 100% respectively.

In addition the percentage of subjects achieving a Response, Complete Response and Platelet Count $\geq 50 \times 10^9/L$ will be plotted at each post-Baseline visit. Separate plots will be presented for each response type with all dose arms overlaid on the same plot.

Analyses will be performed for the FAS and repeated for the PPS. Summary tabulations by dose arm will be repeated for the subgroups defined in [Section 4.8](#) (based on the FAS only). Percentage of days without bleeding will also be described by dose arm for each type of response (response, complete response and platelet Count $\geq 50 \times 10^9/L$). Percentage of days without bleeding is calculated using the following formula:

$$\frac{((N \text{ of visits with a SMOG score} - N \text{ of these visits where bleeding occurred}) / N \text{ of visits with a SMOG score}) \times 100$$

In case rescue medications are taken, only the data up to the start date of rescue medication will be utilized for the summary tables. Listings will contain all the data but a footnote will be included indicating the patients for which some data has been excluded from the summary tables. In case of partial dates, the imputation rules for partial dates described in [Section 4.2.7](#) will be applied.

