8.2 Other efficacy variables

8.2.1 ITP bleeding score

The ITP bleeding score is a consensus-based ITP-specific Bleeding Assessment Tool (ITP-BAT) based on a precise definition of bleeding manifestations and on the grading of their severity (Rodeghiero et al, 2013). The ITP bleeding score will be assessed using the ITP-BAT tool version 1.0 at the visits indicated in [Section 2.2.2](#).

Bleeding manifestations will be grouped into 3 major domains, with gradation of severity (SMOG):

- Skin (S)
- Visible mucosae (M)
- Organs (O)

Each bleeding manifestation is assessed at the time of examination and each domain is subcategorized into different types of bleeding. Severity is graded from Grade 0 to 3 or 4, with Grade 5 for any fatal bleeding. Bleeding reported by the subject without medical documentation is graded as 1. The worst bleeding manifestation since the last visit (or in the 15 days preceding the first visit) is graded for each bleeding type (within each domain), and the highest grade within each domain is reported as part of the SMOG.

The overall SMOG index will be reported as S2M2O3 for example. Intracranial bleeding will always be reported, irrespective of its grade. For example, if a female subject had S2 (subcutaneous hematoma) M2 (epistaxis) O3 (menorrhagia) and an intracranial bleeding Grade 2

(post trauma, requiring hospitalization), the SMOG index is S2M2O3 (intracranial 2). If the same subject also had intracranial bleeding Grade 3, the SMOG index is S2M2O3 (intracranial 3).

Further details regarding the bleeding types and scoring algorithms are provided in [Section 13.3](#).

The individual responses for the ITP bleeding score will be listed by dose arm and visit for those items related to the SMOG score. A separate listing will be presented for the bleeding history obtained at Screening including the date and results of any platelet counts (obtained outside the clinical study) together with any medications taken which may interfere with hemostasis; this information will not form part of the SMOG score. Details of bleeding after surgery, invasive procedures and hemostatic challenges, including platelet counts associated with such procedures will also be listed. This information will not form part of the SMOG score.

A separate listing of the grades for each bleeding type will be presented for each domain, and will include the overall score (highest grade) for the specific domain which will be used in the derivation of the SMOG.

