The results for the ITP bleeding score will be summarized (n, median, minimum and maximum) by dose arm and visit (absolute values only) for each domain. In addition the number and percentage of subjects with severe or clinically relevant bleeding will be summarized at each visit. Clinically relevant bleeding is defined as follows:

- Skin (S) severity of Grade 3
- Mucosal (M) severity of Grade 2 or higher and/or
- Organ (O) severity of Grade 2 or higher

The number and percentage of subjects with absence of bleeding at each visit will also be included in the summary. Absence of bleeding will correspond to a Grade 0 for each domain.

Summaries will be presented for both the FAS and the PPS.

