8.2.1.1 ITP bleeding score and platelet response

In addition to the platelet response variables defined in [Section 8.1.1](#) the following variables will also be defined based on a combination of platelet response and information from the ITP bleeding score (these will be referred to as Clinical Response variables). In case rescue medications or prohibited medications potentially affecting platelet counts are taken, only the platelet data up to the start date of rescue medication will be utilized for the summary tables (refer to [Section 8.1.4](#)):

- **Clinical Response:** a Clinical Response is defined as a platelet count $\geq 30 \times 10^9/L$ with at least 2-fold increase from the Baseline value AND absence of bleeding, by visit. This must be confirmed by a second measurement at least 5 days later (to allow for the ± 2 -day visit window), showing a platelet count $\geq 30 \times 10^9/L$ and at least 2-fold increase from the Baseline.
- **Time to Clinical Response** is defined as the time from starting treatment (Day 1) to achievement of Clinical Response. The will be taken as the time to the first platelet assessment (obtained at the same time as the corresponding ITP bleeding score assessment). If the second assessment does not fulfill the required criteria for a clinical response, the subject will be considered as a nonresponder at the respective visits.

- **Duration of Clinical Response:** the duration of Clinical Response is defined as the time between achievement of a Clinical Response to the first time a loss of Clinical Response occurred (defined as platelet count $<30 \times 10^9/L$ or less than 2-fold increase from Baseline OR presence of bleeding). Refer to Section 8.1.1 in case a subject has several clinical responses or the clinical response is maintained until the end of the study".
- **Complete Clinical Response:** a Complete Clinical Response is defined as a platelet count $\geq 100 \times 10^9/L$ AND absence of bleeding, by visit. This must be confirmed by a second measurement at least 5 days later (to allow for the ± 2 -day visit window), showing a platelet count $\geq 100 \times 10^9/L$.
- **Time to Complete Clinical Response:** the time to Complete Clinical Response is defined as the time from starting treatment (Day 1) to achievement of Complete Clinical Response

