- **Duration of Complete Clinical Response:** the duration of Complete Clinical Response is defined as the time between achievement of a Complete Clinical Response to the first time a loss of Complete Clinical Response occurred (defined as platelet count $<100 \times 10^9/L$ OR presence of bleeding). Refer to Section 8.1.1 in case a subject has several clinical responses or the clinical response is maintained until the end of the study".
- **No Clinical Response or a loss of clinical response:** the platelet count must be defined as a platelet count $<30 \times 10^9/L$ OR $\geq 30 \times 10^9/L$ WITHOUT at least a 2-fold increase from the Baseline value OR presence of bleeding, by visit. This must be confirmed by a second measurement 1 to 9 days* later, showing a platelet count $<30 \times 10^9/L$ OR $\geq 30 \times 10^9/L$ WITHOUT at least a 2-fold increase from the Baseline value.

For all the above response criteria, the calculation rules included in Section 8.1.1 will apply. In addition the following will be applicable:

- The Clinical Response variables will be assessed only for visits for which both platelet counts and the ITP bleeding score are assessed. The last visit cannot be a clinical response as no confirmation after that is available.
- Absence of bleeding is indicated by Grade 0 for all domains of the SMOG, or a Skin Grade of 0 or 1
- Presence of bleeding is indicated by a Mucosae or Organs Grade of ≥ 1 , or Skin Grade of ≥ 2

*This differs from the published definition (Rodeghiero et al, 2009) which requires 2 platelet measurements 1 day apart to define no response or loss of response. In the current protocol platelet count assessments are not as frequently planned (unless unscheduled measurements are performed), thus it was deemed appropriate to modify the definition above to take into account the schedule of assessments in this study.

As a result the following clinical response variables are not in complete accordance with the guideline:

- Duration of Clinical Response
- Duration of Complete Clinical Response
- No Clinical Response

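### Section 8.2.1.1 classes the same visit as both free of bleeding and bleeding, and its No/loss rule cannot confirm a loss caused by bleeding alone

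*SAP*

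**What the plan says.** Clinical Response and Complete Clinical Response (SAP Section 8.2.1.1) each combine a platelet criterion with absence of bleeding at the same visit. The bleeding term is settled by two bullets:

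- Absence: "Absence of bleeding is indicated by Grade 0 for all domains of the SMOG, or a Skin Grade of 0 or 1".
- Presence: the bullet opens "Presence of bleeding is indicated by a Mucosae or Organs Grade of", sets the threshold at 1 or more, and adds a Skin grade of 2 or more.

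Response is confirmed on platelets only: "This must be confirmed by a second measurement at least 5 days later", with the platelet threshold repeated and no bleeding condition.

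No Clinical Response, or its loss, is triggered by a platelet failure or by bleeding; the trigger ends "WITHOUT at least a 2-fold increase from the Baseline value OR presence of bleeding, by visit". Then: "This must be confirmed by a second measurement 1 to 9 days" later, and that second measurement must show a platelet failure. The two Duration bullets in the same section end the response at a platelet failure or at bleeding and state no confirmation. Section 2.2.2 likewise lists bleeding as an alternative to platelet failure, both for loss and for No Clinical Response.

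Two related places:

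- Section 8.2.1, for the bleeding-score summary: "Absence of bleeding will correspond to a Grade 0 for each domain".
- Section 8.1.3.3: "Percentage of days without bleeding is calculated using the following formula". The formula that follows is visits with a SMOG score minus those with bleeding, divided by visits with a SMOG score, times 100.

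**The concern.** The two bleeding bullets should be complements, since every graded visit is either bleeding or not. As worded they overlap, and the overlap contains mucosal and organ bleeding. A programmer who codes Clinical Response from the absence bullet will count a subject with organ bleeding as a responder if the skin grade is 0 or 1. One who codes it as 'not present' will not. The plan does not say which bullet governs.

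The No/loss bullet raises a second problem. Bleeding opens the door to a loss, but only a platelet failure can close it. A subject who bleeds with platelets maintained has lost response under the Duration bullets and Section 2.2.2, and has no confirmed loss under the No/loss bullet.

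At stake are the two clinical response rates (first problem), and the response durations and No/loss classification (second problem).

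**Working it through.** The plan states no figure on this point, so there is none to reproduce. The check applies the rules as written.

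**1. Absence against presence.** Inputs are the two bullets above and the grading in Section 8.2.1: "Severity is graded from Grade 0 to 3 or 4, with Grade 5 for any fatal bleeding". Ranges by domain are an assumption here: S 0–3, M 0–3, O 0–4, then varied.

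- All combinations: 4 × 4 × 5 = 80.
- Literal absence is S ≤ 1 with any M and O: 2 × 4 × 5 = 40. The all-zero branch adds nothing, because S = 0 already qualifies.
- Presence is everything except S0M0O0 and S1M0O0: 80 − 2 = 78.
- Both rules met: 40 − 2 = 38. Neither met: 0.
- Of those 38, clinically relevant bleeding by Section 8.2.1 (M ≥ 2 or O ≥ 2, given S ≤ 1): 2 × (20 − 4) = 32.

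With all domains 0–3 the overlap is 32 − 2 = 30 of 64; with all domains 0–4 it is 50 − 2 = 48 of 125. These count grade combinations, not subjects; they show that the overlap does not depend on the assumed ranges.

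If absence is read as S ≤ 1 and M = 0 and O = 0, it has two members (S0M0O0, S1M0O0) and is the exact complement of presence in all three ranges.

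**2. Loss.** Take a visit with adequate platelets and bleeding, followed by a second measurement 1 to 9 days later:

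| Second platelet count | Bleeding at second visit | Loss by Duration bullet | Confirmed by No/loss bullet |
|---|---|---|---|
| maintained | no | yes | no |
| maintained | yes | yes | no |
| failing | no | yes | yes |
| failing | yes | yes | yes |

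All four are a loss by the Duration bullet; two are a confirmed loss. If the presence bullet governs, the other two are neither a Clinical Response nor a confirmed No Clinical Response at that visit, even when bleeding is recorded twice.

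The footnote to the No/loss bullet explains the 1-to-9-day window by the platelet schedule. It then names both durations among the variables that depart from the published definition as a result. That suggests the confirmation rule feeds the durations, although their own bullets do not say so.

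**3. Scale.** One subject is 1/15 = 6.7 points in Dose Arms 1 and 2, and 1/12 = 8.3 to 1/6 = 16.7 points in Dose Arms 3 to 5 (arm sizes from Section 2.3).

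**4. The percentage.** In Dose Arm 1 the post-Baseline SMOG visits are Days 8, 15, 22, 29, 36, 50, 64 and 85 (Section 2.2.2). Bleeding recorded only at Day 85 gives 7/8 = 87.5%, or 8/9 = 88.9% if a bleeding-free Baseline is counted. Bleeding at Days 8, 15 and 22 gives 5/8 = 62.5%, or 6/9 = 66.7%. The formula does not say whether Baseline counts, and the unit is assessments, not days.

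**The case against.** The strongest reply is that the intent is evident. The presence bullet stands directly below the absence bullet and says that mucosal or organ bleeding is bleeding. The literal reading makes the all-zero branch redundant. Section 14.3.2, Change #17, shows that the superseded rule required Grade 0 everywhere, so the current text looks like a relaxation for Skin Grade 1 only. This stands as evidence of intent. It does not remove the contradiction, because the absence bullet is the term that Clinical Response uses.

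Four stronger readings are tempting, and the document does not support them:

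- **Clinical Response is overstated.** That follows only if the absence bullet is coded literally. If the presence bullet governs, there is no overstatement.
- **The loss rule inflates the response rate.** It does not enter the rate. Response has its own platelet-only confirmation, which bleeding at the confirming visit does not cancel.
- **Section 8.2.1 is a third contradictory rule.** It defines absence for the bleeding-score summary, while the Section 8.2.1.1 rule is scoped to the clinical response criteria. They differ only for S1M0O0, once the intended reading is adopted. That is a matter of labelling.
- **Weighting by interval would recover days.** For the Day 85 example it gives (84 − 21)/84 = 63/84 = 75%, but this assumes bleeding on every day of the interval. SMOG records only the worst manifestation since the last visit, so bleeding days are unknown. Only the word 'days' is wrong; the formula is printed in full and reproducible.

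It is also fair that these are not the leading outputs. The primary variable is treatment-emergent adverse events, the main efficacy variable is maximum platelet increase, the bleeding score serves an exploratory objective, and the tests in Sections 8.1.3.1 and 8.1.3.2 do not use Clinical Response. Domain grades are listed by subject, so conflicting visits would be visible.

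**Conclusion.** The point holds as two defects of definition in Section 8.2.1.1. First, the absence and presence rules overlap for any visit with Skin grade 0 or 1 and mucosal or organ bleeding; Clinical Response and Complete Clinical Response can be overstated if the absence bullet is programmed as written. Second, bleeding with maintained platelets cannot be confirmed as a loss under the No/loss bullet, while the Duration bullets and Section 2.2.2 count it; this affects duration and No/loss status only.

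The size is 6.7 points per reclassified subject at n = 15, up to 16.7 at n = 6. How many subjects are affected, if any, cannot be derived from the document. The overlap itself rests on no assumption beyond reading the bullets as worded; only the counts of grade combinations use assumed ranges. Should-fix, since the outputs are secondary or exploratory.

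**What to change.** - **Absence:** Skin grade 0 or 1, and Mucosae grade 0, and Organs grade 0. State that presence is its complement.
- **Section 8.2.1 summary:** label it 'SMOG Grade 0 in all domains', or align it with this rule.
- **Loss:** apply platelet confirmation only to platelet-based loss. Let bleeding alone count at the visit where it is recorded, so that the No/loss bullet agrees on bleeding with the Duration bullets and Section 2.2.2. State whether the 1-to-9-day platelet confirmation applies to the durations.
- **Section 8.1.3.3:** rename the percentage 'percentage of SMOG assessments without bleeding', say whether Baseline is included, and name the bleeding rule that it uses.

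The cost is SAP wording and derivation code before database lock. No new data are needed. Clinical response rates would be lower than under literal coding only for subjects with mucosal or organ bleeding at an otherwise qualifying visit, and durations could shorten where confirmation would otherwise have been applied to a bleed.

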8.2.2 Patient reported outcomes

8.2.2.1 NFI-MS

The NFI-MS was developed in multiple sclerosis and consists of 23 items in four subscales:

- Physical (8 items)
- Cognitive (4 items)
- Relief by diurnal sleep or rest (6 items)
- Abnormal nocturnal sleep and sleepiness (5 items)

Each item is answered using a 4-point Likert scale according to the following:

- 0 = Strongly disagree
- 1 = Disagree
- 2 = Agree
- 3 = Strongly agree

Within each subscale a summary score is calculated by adding up the responses to each item, i.e., the summary score for the physical subscale ranges from 0 to 24. In addition, an overall summary score (ranging from 0 to 30) is calculated using specified items from the Physical and Cognitive subscales. The individual items and further detail regarding the scoring algorithm are presented in [Section 13.2](#). A listing with the questionnaire glossary will be described.

The individual NFI-MS item results and calculated summary scores (for each subscale and for the Physical/Cognitive subscales) will be listed by dose arm and visit including changes from Baseline (Day 1, predose). Descriptive summaries (including n, arithmetic mean, median, SD, minimum and maximum) will be presented by dose arm and visit for both absolute values and changes from Baseline. Summaries will be presented for both the FAS and PPS.

Mean and change from Baseline values will be plotted over time by dose arm with all dose arms overlaid on the same plot, for both the FAS and PPS. Separate plots will be presented for each individual subscale and the Physical/Cognitive overall score.

9 PHARMACOKINETICS AND PHARMACODYNAMICS

9.1 Pharmacokinetics

Due to the blood sampling regimen there will be no calculation of PK parameters using standard methods eg, noncompartmental analysis. Population PK analysis may be conducted and will be described in a separate Data Analysis Plan and reported outside the CSR.

The actual blood sampling timepoints for UCB7665 concentration will be obtained relative to the start time of the first infusion. No time deviations will be calculated as the blood sampling is not scheduled at a specified timepoint at each visit.

Individual concentrations of UCB7665 will be listed by dose arm for the SS and will include the actual sampling time in days relative to the first dose. The planned dose in mg will be calculated based on the body weight at Screening and the dose arm, and included in the listing. The actual dose administered will be calculated based on the planned dose and the percent of planned dose administered as follows:

$$\text{Actual dose (mg)} = \text{Planned dose (mg)} * \text{Percent of planned dose administered}$$

The percent of planned dose administered is calculated as described in [Section 10.1](#). The actual dose will also be included in the concentration listing.

Individual concentrations will be summarized by dose arm and scheduled sampling day for the PK-PPS using n, arithmetic mean, median, SD, minimum, maximum, geoMean and 95% CI, geoCV (assuming log-normally distributed data).

For each subject, individual concentration versus time (day) profiles will be presented graphically in linear and semi-logarithmic scale. Individual plasma concentration versus time (day) profiles will also be displayed for each dose arm with all subjects within each dose arm overlaid on the same plot (linear and semi-logarithmic scale).

Geometric mean profiles of UCB7665 with corresponding lower and upper limit of the 95% CI (linear scale plot only) will also be presented with all dose arms overlaid on the same plot.

All figures will include the LLOQ on the semi-logarithmic plots.

The following rules will apply for PK data listings and summaries:

- Values below the LLOQ will be reported as BLQ in the listings
- Descriptive statistics of concentrations will be calculated if at most 1/3rd of the individual data points are missing or are not quantifiable (<LLOQ). Values that are BLQ will be replaced by the numerical value of the LLOQ/2 in this instance. However if n≤3, then only n, minimum and maximum will be presented. The other descriptive statistics will be left blank.
- If no subjects have data, only n=0 will be presented. The other descriptive statistics will be left blank.

The 95% CI for the geoMean will be calculated by obtaining the lower and upper 95% CI for the arithmetic mean on the log-transformed data and back-transforming to obtain the respective values for the geoMean

- The 95% CI lower and 95% CI upper should be left blank if the SD (or equivalently, the geoCV) is 0

- The geoCV will be calculated using the following formula where SD is the standard deviation from the log-transformed data

$$\text{geoCV (\%)} = \text{sqrt}[(\text{exp}(\text{SD}^2) - 1)] \times 100$$

The above summaries will be repeated separately for the subjects in the PK/PD substudy sample, in the event of very few subjects (<5 subjects) only listings will be provided.

Further analyses and summaries relating to the population PK analyses and PK/PD analyses will be described in a separate SAP and reported separately.

9.2 Pharmacodynamics

The analysis of the PD data will be performed on the FAS with the exception of the total IgG and IgG subclasses, which will be analyzed on the PD-PPS. All listings will be presented for the SS.

The above summaries will be repeated separately for the subjects in the PK/PD substudy sample, in the event of very few subjects (<5 subjects) only listings will be provided.

